13.1 Sample size estimates

This study was a cohort study of prospective, multicenter, hospital-based, continuous enrollment patients. It is planned to choose three hospitals in Beijing. The investigation and registration of the ending events are carried out through hospital follow-up examinations, investigations, registration and hotline reports, face-to-face or telephone follow-up, and monitoring information database supplementation.

Sample size and power were calculated based on previous studies and postoperative neurological complications, which were much better to indicate the efficacy of RIPC.

We calculated the simple size and power with PASS, version 11 (NCSS, LLC, Kaysville, UT, USA). We expected $\approx 10\%$ of subjects in the RIPC group and 20% of subjects in the other 2 groups would have new postoperative neurological complications. The intended target sample size was 328 subjects allowing 15% loss to follow-up and with 90% power and an α of 0.05 (2-sided) of significance.

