Secondary endpoint	
 • The severity of the ischemic stroke after surgery • Number of patients occurred restroke at Follow-up Period • Number of patients dependent or death at follow-up period • Number of patients with improved neurological function at follow-up period • Perfusion status of patients at follow-up period • Number of patients with any side effects of remote ischemic preconditioning (RIPC) treatment.
Inclusion Criteria	
 • Patients who diagnosed with moyamoya disease • Adults 18 to 65 years of age • The onset symptoms manifested as ischemic symptoms (TIA or stroke) or atypical symptoms (headache, epilepsy or asymptomatic) • Able to receive the necessary imaging examination • Patients who pre-agreed to the study
Exclusion Criteria	
 • Prior cerebral hemorrhage history • Other brain or cerebrovascular disease • Previous history of revascularization surgery • Dependent (mRS > 2) • Receive other type of revascularization surgery • Peripheral blood vessel disease (especially subclavian arterial and upper limb artery stenosis or occlusion).

	
 • Patients who do not agree with the study
Sample Size	
Sample size and power were calculated based on previous studies and postoperative neurological complications, which were much better to indicate the efficacy of RIPC. We calculated the simple size and power with PASS, version 11 (NCSS, LLC, Kaysville, UT, USA). We expected ≈10% of subjects in the RIPC group and 20% of subjects in the other 2 groups would have new postoperative neurological complications. The intended target sample size was 328 subjects allowing 15% loss to follow-up and with 90% power and an α of 0.05 (2-sided) of significance.

Follow-up	
The face-to-face interview will be performed by study neurologists at discharge, at 6 months and at 12 months (or by telephone) after the recruitment of patients.

2. Study Rationale

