
4. Study Plan and Procedure

Study Design and Flow Chart

This study was a multi-center, prospective, randomized, controlled trial of

randomized (1:1) adult ischemic MMD patients undergoing indirect revascularization into two groups:

1. RIPC group

Remote limb ischemic preconditioning (RIPC) is consisted of five 5-min cycles of bilateral arm ischemia/reperfusion, it is induced by a sphygmomanometer placed on bilateral arm and inflated to 200 mmHg for 5-min followed by deflating the cuff for 5-min, patients in the RIPC group will do it twice a day for at least five days before EDAS.

2. sham RIPC group

Sham RIPC group is consisted of five 5-min cycles of bilateral arm ischemia/reperfusion, induced by a sphygmomanometer placed on bilateral arm and inflated to 60 mmHg for 5-min followed by deflating the cuff for 5-min, they will do it twice a day for at least five days before EDAS.

5. Study Endpoints

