13.2 Statistical Analyses

The results of the study were analyzed using IBM SPSS Statistics 23.0 (IBM Corp, Armonk, NY, USA) data analysis software. Charting was performed using GraphPad Prism 7.0a (GraphPad Software, La Jolla, CA, USA). Continuous variables obeying the normal distribution were expressed as mean \pm standard deviation, and two independent sample t-tests or paired t-tests were used for comparison between the two groups. Continuous variables with unknown distributions were expressed using median and interquartile range and compared between the two groups by Mann-Whitney U test or Wilcoxon rank sum test. The normality of the continuous variables

was tested using the Shapiro-Wilk W test. The categorical variables were expressed as frequency and percentage, and comparisons between the two groups were made using the Pearson chi-square test or the McNemar paired chi-square test. Correlation between the two variables was analyzed using Pearson, Kendall's tau-b or Spearman correlation coefficients according to the corresponding variable types. Prognostic information was analyzed by Kaplan-Meier survival analysis based on least squares method and compared between the two groups using log-rank test. All statistical tests were two-sided, and the results were considered statistically significant at $P < 0.05$.

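### Read as a total, 328 subjects gives about 65% power after the planned 15% loss (72% with none) for 10% versus 20%, not the stated 90%

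*Combined protocol and SAP*

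**What the plan says.** The sample size paragraph appears twice with the same content, in section 1 (Protocol Synopsis, Sample Size) and in section 13.1.

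- Assumed rates: "We expected ≈10% of subjects in the RIPC group and 20% of subjects in the other 2 groups" would have new postoperative neurological complications.
- Target: "The intended target sample size was 328 subjects allowing 15% loss to follow-up and with 90% power". The text does not say per group or per arm, so it reads as the trial total.
- Significance level: 0.05, two-sided. The software named is PASS version 11; the procedure and its settings are not given.
- Design (Synopsis and section 4): "randomized (1:1) adult ischemic MMD patients undergoing indirect revascularization into two groups", namely RIPC and sham RIPC.
- Test (section 13.2): for categorical variables, "comparisons between the two groups were made using the Pearson chi-square test", with a McNemar test for paired data. No continuity correction is mentioned.

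**The concern.** Detecting 10% against 20% with 90% power normally takes more than 500 evaluable patients, so a total of 328 that already includes an allowance for loss looks about half of what is needed. The paragraph also speaks of "20% of subjects in the other 2 groups would have new postoperative neurological complications", which does not fit a trial with a single comparison arm.

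The ethics committee, the DSMB and later readers will take the 90% at face value. If 328 is the total, the chance of missing the effect the trial was designed to find is about three times the stated 10%, and a non-significant result would say much less than the protocol implies. If 328 is per arm, the recruitment target as printed is wrong by a factor of two.

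**Working it through.** **Inputs, all from the documents.** p1 = 0.10, p2 = 0.20, so δ = 0.10 and the mean rate p̄ = 0.15; two-sided α = 0.05 (z = 1.960); power 90% (z = 1.2816); loss 15% (Synopsis and section 13.1). Two arms, 1:1 (Synopsis and section 4). Pearson chi-square test (section 13.2).

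**Step 1: try to reproduce 328.** Evaluable patients per arm:

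n = [1.960·√(2·0.15·0.85) + 1.2816·√(0.10·0.90 + 0.20·0.80)]² / 0.10²
= (0.9897 + 0.6408)² / 0.01 = 265.9, rounded up to 266.

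The total is 2 × 266 = 532 evaluable. Allowing for loss, 532 / 0.85 = 626 randomised (532 × 1.15 = 612 with the cruder inflation).

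With continuity correction, n′ = (n/4)·[1 + √(1 + 4/(n·δ))]² = 285.5, rounded up to 286 per arm. That is 572 evaluable and 673 randomised (658 with × 1.15).

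Other settings, as totals:

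| Setting | Evaluable | Randomised (÷ 0.85) |
|---|---|---|
| Two-sided, 90%, unpooled variance | 526 | 619 |
| Two-sided, 90%, arcsine | 522 | 615 |
| Two-sided, 80%, pooled | 398 | 469 |
| One-sided, 90%, pooled | 434 | 511 |
| One-sided, 80%, pooled | 314 | 370 |

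None gives 328 as a randomised total.

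**Step 2: power of 328 as a total.** Power = Φ{[δ√n − 1.960·√(2p̄(1−p̄))] / √(p1(1−p1) + p2(1−p2))} = Φ{[0.10·√n − 0.9897] / 0.5}.

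- After 15% loss: 328 × 0.85 = 278.8, about 139 per arm. Φ{(1.1790 − 0.9897)/0.5} = Φ(0.378) = 64.7%. Exact binomial enumeration of the uncorrected Pearson test gives 65.5%.
- No loss: 164 per arm. Φ{(1.2806 − 0.9897)/0.5} = Φ(0.582) = 72.0%; exact 72.6%.
- Check on the formula: 266 per arm gives 90.0%.

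**Step 3: what 279 evaluable patients can detect.** With 139 per arm and a control rate of 20%, power reaches about 90% when the RIPC rate is about 6.8%. With the RIPC rate held at 10%, it takes a control rate of about 24.6%.

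**Step 4: the per-arm reading.** The continuity-corrected size times 1.15 is 285.5 × 1.15 = 328.3 (327.75 from 285, 328.9 from 286). If 328 is per arm (656 in total), about 279 per arm remain after loss, and power is Φ{(1.6703 − 0.9897)/0.5} = Φ(1.361) = 91.3%.

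**Step 5: a three-group reading.** Splitting 328 equally over three groups gives, even with no loss, 64% power for RIPC against two pooled control groups and 54% for RIPC against one of them. The reference to two other groups therefore does not explain the stated 90%.

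**The case against.** The power discrepancy itself has no good answer: both statements of the sample size agree with each other, nothing is blacked out, and no other section gives a different number. The fair objections concern what is built around it.

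- **The per-arm explanation is an inference.** It needs a continuity correction that section 13.2 does not mention, and inflation by 1.15 rather than division by 0.85. Without the correction the per-arm figure is 313 (or 306); with it and proper inflation, 337. Other explanations also fit: continuity-corrected 10% versus 24% needs 164 per arm, exactly 328 in total before any loss. This stands. The per-arm reading is a likely explanation, not an established one.
- **The 65% assumes the full 15% loss.** The primary endpoints fall within 30 days of surgery, while follow-up runs to 12 months, so loss may be smaller for the primary analysis. At 5% loss (about 156 per arm) power is about 70%. This stands as a qualification, but even with no loss power is 18 points below the stated figure.
- **The mention of two other groups may be only a wording slip.** The two assumed rates can still be applied to RIPC against sham, as they are here. That is fair; the phrase still contradicts the two-arm design and needs correcting.

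**Conclusion.** The concern holds. As written, the sample size, the assumed rates and the power are inconsistent. A total of 328 gives about 65% power after the plan's own loss allowance and 72% at best, which means a type II error of 28% to 35% instead of 10%. Ninety per cent power for 10% versus 20% needs 532 evaluable patients (626 randomised).

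This rests on the documents' own rates, alpha, allocation and test, and on reading 328 as the total, which is what the text says. The choice of formula does not matter: at two-sided 0.05 and 90% power, the evaluable total lies between 522 and 572 under every method tried. Whether the true slip was a per-arm figure or a mis-stated control rate cannot be settled from the documents.

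**What to change.** Ask the sponsor whether 328 is the total or per group, and for the PASS procedure and settings. Then correct the Synopsis and section 13.1 together:

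- **If 328 is the total:** restate power for 10% versus 20% as about 65% after 15% loss and 72% with none, or state the difference detectable with 90% power after that loss (20% versus about 6.8%).
- **If 328 is per group:** write 328 per group, 656 in total, with about 91% power after 15% loss.
- **In both cases:** name the comparator as the sham RIPC group, and say whether a continuity correction was used.

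Restating the power costs protocol wording only and adds no patients; the price is a less favourable figure. The per-group correction is also only wording if sites were already planning for 656. If they were planning for 328, it doubles recruitment, and the sponsor would have to weigh that against accepting the lower power.

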13.2 Statistical Analyses

The results of the study were analyzed using IBM SPSS Statistics 23.0 (IBM Corp, Armonk, NY, USA) data analysis software. Charting was performed using GraphPad Prism 7.0a (GraphPad Software, La Jolla, CA, USA). Continuous variables obeying the normal distribution were expressed as mean \pm standard deviation, and two independent sample t-tests or paired t-tests were used for comparison between the two groups. Continuous variables with unknown distributions were expressed using median and interquartile range and compared between the two groups by Mann-Whitney U test or Wilcoxon rank sum test. The normality of the continuous variables

was tested using the Shapiro-Wilk W test. The categorical variables were expressed as frequency and percentage, and comparisons between the two groups were made using the Pearson chi-square test or the McNemar paired chi-square test. Correlation between the two variables was analyzed using Pearson, Kendall's tau-b or Spearman correlation coefficients according to the corresponding variable types. Prognostic information was analyzed by Kaplan-Meier survival analysis based on least squares method and compared between the two groups using log-rank test. All statistical tests were two-sided, and the results were considered statistically significant at $P < 0.05$.

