5.2 Clinical Secondary Endpoint

- The severity of the ischemic stroke after surgery

- Number of patients occurred restroke at follow-up period
- Number of patients dependent (mRS > 2)or death at follow-up period
- Number of patients with improved neurological function at follow-up period
- Perfusion status of patients at follow-up period
- Number of patients with any side effects of remote ischemic preconditioning (RIPC) treatment.

6. Patient Selection Criteria

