6.2 Exclusion Criteria

- Prior cerebral hemorrhage history
- Other brain or cerebrovascular disease
- Previous history of revascularization surgery
- Dependent (mRS > 2)
- Receive other type of revascularization surgery

- Peripheral blood vessel disease (especially subclavian arterial and upper limb artery stenosis or occlusion).
- Patients who do not agree with the study

7. Informed Consent

The principles of Informed Consent, according to FDA Regulations and ICH guidelines on GCP, will be followed. Investigator will submit a copy of the proposed consent form, together with the study protocol, to the central Institutional Review Board (IRB) at Beijing Tiantan Hospital for approval. Each eligible patient who wishes to participate in this study will be invited to give written informed consent. Before the consent is signed, a trained researcher will explain study purpose, description, duration, potential risks and anticipated benefits, cost and compensation, voluntary nature of participation, appropriate alternatives, treatment for study-related injury, whom to contact with questions or concerns or study-related injuries, maintenance of confidentiality of record, and funding source. Patients will be encouraged to consent for the blood drawing for biomarker testing only if they would be prepared to enroll in the trial.

8. Enrollment of Patients

All patients with moyamoya disease who visit the research center will be asked if they are involved in the study as long as they meet the inclusion criteria. This study is included in patients who have voluntarily participated in the study and signed

informed consent and did not meet the exclusion criteria.

9. Randomization of Patients

Patients was randomized by random number table

10. Image Data Evaluation

In this study, Suzuki staging was determined by DSA technique; subarachnoid hemorrhage, ischemic stroke (cerebral infarction), and cerebral hemorrhage were diagnosed using the Fourth National Conference on Cerebrovascular Diseases (1995).

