In order to prevent errors in the research due to the interpretation technique, this study set up a decision-making committee to uniformly judge the imaging data of the patients enrolled. Two experienced neuroimaging physicians conducted mutual blind interpretation, and the results of the inconsistent report should be ranked third. The senior neuroimaging chief physician will conduct a trial and finally submit true and reliable imaging results for all cases. The interpreter does not participate in the study design and does not know the patient's clinical information.

11. Bio sample test

Blood samples were drawn from the cubital vein; the points of measurement included baseline, pre-EDAS, right 1 hour and 24 hours post-EDAS. The collected blood samples were sent for examination, and plasma neuron specific enolase (NSE) and human S protein 100B (S-100B) levels were examined in the test samples.

11. Schedule of Follow-up and Post-study Follow-up Period

All patients will be followed up until the primary endpoint or the end of the trial.

Complete endpoint information will be obtained with the best effort irrespective of patient study status, unless patients withdraw consent to participate the trial. The face-to-face interview will be performed by study neurologists at discharge, at 6 months and at 12 months (or by telephone) after the recruitment of patients.

Visits	Windows	Definition
Randomization	0 day	Study Day 0 day
At discharge	0 day	Based on the number of hospitalization days
At 6 months	14 days	Day 166-194
At 12 months	30 days	Day 330-390

12. Quality Assurance

Periodic monitoring and auditing will be performed at each site to ensure that data generated during the study reflect what is specified in the protocol, and data consistence by comparing data in the case report form (CRF) and data collected in source documents for (CRF vs. source documents). If patients who have events go to non-study sites for treatment, source documents will be photocopied for review. It should be guaranteed that the study investigators and relevant study personnel are available during the monitoring visits and possible audits.

13. Statistical Consideration

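### Section 13.2 offers the paired t-test and McNemar test for comparing two randomised arms that contain no pairs (wording error, minor)

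*Combined protocol and SAP*

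**What the plan says.** Section 13.2 (Statistical Analyses) assigns tests by type of variable, not by endpoint.

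- Normal continuous variables: "two independent sample t-tests or paired t-tests were used for comparison between the two groups".
- Other continuous variables: "compared between the two groups by Mann-Whitney U test or Wilcoxon rank sum test". Both of these are unpaired.
- Categorical variables: "comparisons between the two groups were made using the Pearson chi-square test or the McNemar paired chi-square test".

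The design is a parallel one. Section 4 describes "randomized (1:1) adult ischemic MMD patients undergoing indirect revascularization into two groups", and the whole of section 9 is "Patients was randomized by random number table". No section mentions matched pairs, matching factors or a crossover.

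The two primary endpoints in section 5.1 (cerebrovascular events, and death or dependency, each within 30 days of surgery) are naturally yes/no for each patient. Section 13.1 sizes the trial on two proportions.

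The documents do contain repeated measurements on the same patient. For NSE and S-100B, the bio sample section says "the points of measurement included baseline, pre-EDAS, right 1 hour and 24 hours post-EDAS". The visit schedule in the appendix has mRS at successive visits and CTP before and after surgery. Section 13.2 does not link the paired tests to any of these.

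**The concern.** A paired t-test or McNemar test needs to know which sham patient belongs with which RIPC patient. Here nothing defines that link, so two of the tests named for the between-arm comparison do not fit the design. Section 13.2 gives no rule for choosing between Pearson and McNemar, so the open choice reaches the primary endpoints.

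Three things are at stake. The p-value would depend on an arbitrary ordering of patients. Patients would have to be dropped whenever the evaluable arms differ in size. And the primary test is not fixed in advance.

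A smaller, related point concerns the secondary endpoint "Perfusion status of patients at follow-up period". Pre-surgery CTP is scheduled, but 13.2 names no baseline-adjusted comparison. This matters only if perfusion is analysed on a continuous scale, which the plan does not state.

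**Working it through.** The plan gives no figure on this point. The check is of wording against design, followed by an estimate of what the inapplicable option could do.

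**Inputs.** Section 13.1: "The intended target sample size was 328 subjects allowing 15% loss to follow-up", with expected rates of 10% (RIPC) and 20% (comparator). Section 13.2: two-sided, P < 0.05. Evaluable patients: 328 × 0.85 = 278.8, taken as 139 per arm. Whether 328 is the right total is a separate question and is not used here.

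**Can all patients be paired?** Starting from 164 per arm with independent 15% loss, the chance of equal evaluable arms is the sum of the squared Binomial(164, 0.85) probabilities, which is 0.062, or about 6%. If allocation is a simple coin toss it is about 2%. Otherwise a paired test leaves patients out.

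**A borderline result: 14/139 against 26/139 (illustrative counts).**

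Pearson: the difference is 12/139 = 0.0863 and the pooled rate is 40/278 = 0.1439. Then χ² = 0.0863² / (0.1439 × 0.8561 × 2/139) = 4.205, p = 0.040.

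McNemar on an arbitrary pairing: let k be the number of pairs in which both patients have an event. The discordant counts are 14 − k and 26 − k, so the uncorrected statistic is 12²/(40 − 2k). Under random pairing k is hypergeometric (139, 14, 26).

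| k | Probability | Statistic | p |
|---|---|---|---|
| 0 | 0.047 | 3.60 | 0.058 |
| 1 | 0.170 | 3.79 | 0.052 |
| 2 | 0.274 | 4.00 | 0.046 |
| 3 | 0.258 | 4.24 | 0.040 |
| 4 | 0.158 | 4.50 | 0.034 |
| 5 | 0.067 | 4.80 | 0.028 |

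These rows cover about 97% of random pairings. The share with p above 0.05 is 0.047 + 0.170 = 0.217, or 22%.

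**A result at the plan's own rates: 14/139 against 28/139.** Pearson p = 0.019. The largest McNemar p comes at k = 0. Uncorrected, 14²/42 = 4.67 gives p = 0.031. Continuity-corrected, 13²/42 = 4.02 gives p = 0.045. The exact version gives p = 0.044. No pairing exceeds 0.05.

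**Average behaviour, 139 per arm, enumerating event counts and random pairings.** Each McNemar version is set against its unpaired counterpart.

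| Version | Unpaired power | McNemar power | Loss (points) |
|---|---|---|---|
| Uncorrected | 65.5% (Pearson) | 65.1% | 0.4 |
| Continuity-corrected | 59.0% (Yates) | 58.2% | 0.8 |
| Exact | 59.7% (Fisher) | 58.5% | 1.2 |

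With both arms at 15%, McNemar rejects in 5.0% (uncorrected), 3.2% (corrected) and 3.3% (exact) of trials. With both arms at 10%, a simulation of 100,000 trials gives 5.4% for uncorrected McNemar, against 4.9% for Pearson.

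**Perfusion, if continuous.** The variance of the ANCOVA comparison relative to a follow-up-only comparison is 1 − r², where r is the correlation between baseline and follow-up. The documents give no r. Assuming 0.3, 0.5 or 0.7, the variance is 9%, 25% or 49% lower.

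**The case against.** The strongest reply is that 13.2 is a generic list, not a plan to pair arms. The unpaired test comes first in each sentence, Pearson chi-square is already named, and no pair identifier exists. The natural pairs in the documents are within patients (blood draws, mRS, CTP), so the paired tests were probably meant for those. Much of this stands, and it is why the point is minor. It does not remove the error: the text attaches the paired tests to the comparison of the two groups, and no section restricts them to within-patient change.

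A reader might infer more than the documents support:

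- **That the primary endpoints will be analysed by McNemar.** The plan leaves that option open but does not choose it.
- **That the false-positive rate is inflated.** If the pairing is fixed without sight of outcomes, it is close to 5% or below it.
- **That p could be as low as 0.0005 in the 14 against 26 example.** That requires all 14 RIPC events to be paired with sham events, which has probability of about 1.6 × 10⁻¹² under random pairing.
- **That pairing usually destroys significance.** Corrected and exact McNemar exceed 0.05 in 91% of random pairings of that example. But the same table without any pairing gives 0.060 (Yates) and 0.059 (Fisher), so most of this comes from the correction or exact method, not from pairing.

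It is also fair to say that the perfusion point is a different matter from the paired tests and is conditional on an unstated scale.

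**Conclusion.** Section 13.2 is wrong as written: the paired t-test and McNemar test do not apply to a comparison of unmatched randomised arms, and nothing keeps McNemar away from the binary primary endpoints. Confidence in this wording point is high.

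Severity is minor. The design and the valid tests are both in place. What remains is an inapplicable option and an unfixed choice that could move a borderline result across 0.05.

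The figures assume 139 evaluable patients per arm, the plan's 10% and 20% rates, primary endpoints analysed as yes/no, and a pairing made at random. The borderline counts were chosen to lie near the threshold and do not represent the expected result. The ANCOVA gain rests on assumed correlations and a continuous perfusion measure, and does not apply to a graded one.

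**What to change.** In section 13.2:

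- For between-arm comparisons, name only independent-sample tests, and state that the binary primary endpoints are compared by Pearson chi-square.
- Restrict the paired t-test and McNemar test to within-patient change, for example across blood draws or between CTP before and after surgery. State that these results are descriptive and are not evidence of a treatment effect, because a change within one arm does not compare the arms.
- Secondary: state how perfusion is measured. If it is continuous, compare arms by ANCOVA with the pre-surgery CTP value as covariate. Say how missing follow-up CTP will be handled, since the 12-month contact may be by telephone.

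The cost is SAP wording only. The changes call for no additional patients, visits or measurements, because the blood draws and CTP are already scheduled.
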